Suppose Y_{ij} is the BPF value for the i th patient ($i = 1, \dots, N$) at the j th month ($j = 1, \dots, n_i$), t_{ij} denotes time in weeks, P stands for placebo, and T stands for treatment. Assuming linear change over time, the LMM can be written as the following,

$$Y_{ij} = \alpha_P + \beta_P t_{ij} + (\gamma + \delta t_{ij})g_i + (a_i + b_i + \epsilon_{ij}) \quad (1)$$

where g_i is a dummy variable for group,

$$g_i = \begin{cases} 0 & \text{if } P, \\ 1 & \text{if } T. \end{cases}$$

In Equation (1), α_P , β_P , γ , and δ are fixed effects; α_P is the intercept for the placebo group, β_P is the slope for the placebo group, $\gamma = \alpha_T - \alpha_P = 0$ is the difference of the intercepts, and $\delta = \beta_T - \beta_P$ is the difference of the slopes. Setting $\gamma = 0$ constrains the baseline means to be equal, which controls for initial imbalance that occurs in empirical randomization (Senn, 2013). The terms a_i and b_i are random effects (random intercepts and slopes, respectively), and ϵ_{ij} is random error. We make the typical assumptions

$$[a_i \ b_i]^T \sim \mathcal{N}(\mathbf{0}, \mathbf{G}), \epsilon_{ij} \sim \mathcal{N}(0, \sigma^2 \mathbf{I}_i), \text{ and } [a_i \ b_i]^T \perp \epsilon_{ij}.$$

The prime object of inference is δ , as this is the index of longitudinal activity of T versus P , namely, the difference in rates of change. The null hypothesis of no longitudinal ibudilast effect (equality of T and P slopes) is $H_0: \delta = 0$, and can be evaluated with the likelihood ratio test, or a Z -test, provided a sufficiently large sample size that is provided in the proposed study ($N = 250$, see Sample Size Justification below). The Z statistic is $Z = \hat{\delta}/SE(\hat{\delta})$ and leads to the rejection of H_0 when $|Z| > Z_{1-\alpha}$, with the latter value being the $100 \cdot (1 - \alpha)$ th quartile of the standard normal distribution (single-tailed test).

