significant cross-sectional correlations between whole brain atrophy and overall clinical disability (Fisher, 2011a; Fisher, 2011b). Whole brain atrophy (WBA) also correlates with cognitive impairment (Edwards et al, 2001; Rao et al, 1985; Hohol et al, 1997; Benedict et al, 2004; Lazeron et al, 2005), depression (Feinstein et al, 2004), fatigue (Marrie et al, 2005; Tedeschi et al, 2007), and quality of life (Janardhan & Bakshi, 2000; Rudick et al, 2001). Multivariate analysis suggests that disability correlates better with WBA than with lesion measures (Benedict et al, 2004). WBA progresses over the course of MS, with a mean rate in untreated MS patients generally ranging from 0.5-1.5% per year (Fisher, 2011b). Although one small (n=21) early study found atrophy to slow in later disease (Fox et al, 2000), contemporary studies with larger sample sizes (n=69 and n=963) found similar or faster rates of atrophy in PMS compared with RRMS (Fisher et al, 2008; De Stefano et al, 2010). Atrophy progression in PPMS is similar to SPMS (Kalkers et al, 2001). Longitudinal studies found patients with greater rates of atrophy are more likely to worsen clinically (Dastidar et al, 1999; Molyneux et al, 2000; Fisher et al, 2000; Fisher et al, 2002; Dalton et al, 2004; Minneboo et al, 2008; Di Fillippo et al, 2010). For example, a longitudinal study found WBA progression is predictive of cognitive deterioration (Amato et al, 2007). These clinical correlations appear to be stronger later in the disease (i.e., SPMS compared to RRMS – Fisher et al, 2000; Ge et al, 2000). Altogether although additional treatment trial data is needed, face validity, concurrent validity, and predictive validity of WBA in PMS are significant enough to use it as the primary outcome metric in PMS trials. Based on accumulated evidence, an international consensus panel recommended WBA as the primary outcome of phase II PMS trials (Barkhof et al, 2009). Indeed, several recent PMS studies used WBA as the primary outcome, including trials evaluating lamotrigine (Huang et al, 2002) and simvastatin (Chataway et al, 2012). For currently available RRMS therapies, the treatment effects on atrophy range from 30%-50% compared to placebo, including a 34% slowing of atrophy in a phase II trial of Ibudilast in RRMS (Barkhof et al, 2010) and a 49% slowing over 2 years with simvastatin in SPMS (Chataway et al, 2012).

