7. PRIMARY ANALYSES

7.1. *Primary Objective #1: Evaluate the activity of Ibudilast (MN-166: 100 mg/day) versus placebo at 96 weeks as measured by quantitative MRI analysis for whole brain atrophy using brain parenchymal fraction (BPF).*

The first primary objective of the proposed study is to evaluate the activity of Ibudilast (MN-166) versus placebo by assessing the difference in rates of change in brain parenchymal fraction (BPF) between the Ibudilast and placebo treatment groups as measured at baseline, weeks 24, 48, and 96 post randomization. The evaluation of activity is defined as the test of the null hypothesis that the BPF rates of change in the treatment and placebo groups are equal.

The raw data will be summarized graphically, and in the following table:

Table 7.1: Descriptive statistics of BPF over time

Visit	Ibudilast	Placebo
Baseline		
Mean (SD)	x.xx (xx)	x.xx (xx)
Min. – max.	x.xx-x.xx	x.xx-x.xx
missing	xx	xx
Week 24		
Mean (SD)	x.xx (xx)	x.xx (xx)
Min. – max.	x.xx-x.xx	x.xx-x.xx
missing	xx	xx
Week 48		
Mean (SD)	x.xx (xx)	x.xx (xx)
Min. – max.	x.xx-x.xx	x.xx-x.xx
missing	xx	xx
Week 72		
Mean (SD)	x.xx (xx)	x.xx (xx)
Min. – max.	x.xx-x.xx	x.xx-x.xx
missing	xx	xx
Week 96		
Mean (SD)	x.xx (xx)	x.xx (xx)
Min. – max.	x.xx-x.xx	x.xx-x.xx
missing	xx	xx

The null hypothesis can be evaluated based on an assessment of parameter estimates from a linear mixed model (LMM: Laird and Ware, 1982). LMMs are advantageous for longitudinal clinical trials because they can account for dependency due to repeated measures with relatively few parameters, which potentially enhances statistical efficiency. Furthermore, LMMs can accommodate incomplete cases (i.e., missing data), which is expected in this study due to dropout. LMMs are typically estimated using maximum likelihood methods (Verbeke and Molenberghs, 2000) that yield valid inferences with incomplete cases under the widely applicable assumption that the missing data are ignorable (Little and Rubin, 2002).

For this analysis, assuming linear change over time, the LMM can be written in the following manner:

$$Y_{ij} = \alpha + \beta_1 x_{1i} + \beta_2 x_{2i} + \beta_3 t_{ij} x_{3i} + \beta_4 t_{ij} x_{4i} + a_i + b_i + \epsilon_{ij}$$

where:

- Y_{ij} is the BPF value for the j^{th} subject at the j^{th} time point
- α is the common intercept parameter
- t_{ij} denotes time (in weeks)

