- $x_{1i} = 1$ if the subject was thought to be receiving immunomodulation therapy at randomization (IFN/GA), and 0 if the subject was not thought to be receiving immunomodulation therapy
- $x_{2i} = 1$ if the subject was thought to have primary progressive MS at randomization, and 0 if the subject was thought to have secondary progressive MS
- $x_{3i} = 1$ if the subject is in the treatment group
- $x_{4i} = 1$ if the subject is in the placebo group
- a_i and b_i are random effects (random intercepts and slopes)
- ϵ_{ij} is a random error term

After randomization, it is expected that a small number of enrolled subjects may be discovered to fall into a different stratum than that which was thought to be true at the actual time of randomization. For any such subjects, the true strata value discovered post-randomization (not the value thought to be true at the time of randomization) will be used for the models.

Assuming a common intercept constrains the baseline means to be equal, which controls for any initial imbalance that might occur due to empirical randomization (Senn, 2013). We make the typical assumptions:

$$\begin{bmatrix} a_i \\ b_i \end{bmatrix} \sim N(\mathbf{0}, \mathbf{G}), \quad \varepsilon_{ij} \sim N(0, \sigma^2 \mathbf{I}_i), \quad \text{and} \quad \begin{bmatrix} a_i \\ b_i \end{bmatrix} \perp \varepsilon_{ij}$$

In this model, the parameters β_1 and β_2 are included to adjust the model for the two stratification variables (immunomodulation therapy status at randomization & disease status at randomization). The main parameters of interest are β_3 and β_4 , which correspond to the estimated slopes in the treatment and placebo groups, respectively. The desired test of interest can be obtained by testing the null hypothesis of the following contrast:

$$H_0: \theta_1 = \beta_4 - \beta_3 = 0$$

against the alternative

$$H_1: \theta_1 \neq 0.$$

This null hypothesis can be evaluated with the likelihood ratio test, or a Z-test, provided a sufficiently large sample size which is provided in the proposed study. The Z statistic of interest is:

$$Z = \hat{\theta}_1 / SE(\hat{\theta}_1),$$

and leads to the rejection of H_0 when

$$|Z| < Z_{1-\alpha/2}$$

with the latter being the $100(1-\alpha/2)^{\text{th}}$ quartile of the standard normal distribution.

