If we fail to reject H_0 , then we will conclude that there is no significant difference in the change of BPF between the treatment group and the placebo group over 2 years. If H_0 is rejected in favor of the alternative, and θ_1 is greater than zero, then we will conclude that the study provides evidence that the rate of BPF change is slower in the Ibudilast treatment group relative to the placebo group. However, if H_0 is rejected in favor of the alternative, and θ_1 is less than zero, then we will conclude that the study provides evidence that the rate of BPF change is faster in the Ibudilast treatment group relative to the placebo group. It is important to note that failure to reject the null hypothesis does not imply acceptance of the null hypothesis of no difference in slopes over time for the two groups.

The data from the fitted model will be summarized graphically, and in the following table:

Table 7.2: Estimated rate of BPF change by treatment group

Treatment group	Estimated rate of BPF change 90% CI	p-value for difference in rate of change
Ibudilast	xx (xx, xx)	0.xx
Placebo	xx (xx, xx)	

Since the longitudinal measurements will span up to five time points per participant (baseline, 24, 48,

72, and 96 weeks), there is a possibility that the BPF trajectories will not be linear. In order to assess the sensitivity of the results to the assumption of linearity, non-linear trends will be modeled by inserting time as a categorical variable. For this modelling approach, visits that were performed outside of an expected scheduled visit will be categorized into the next expected scheduled visit. We will compare model fit between the non-linear and linear models using the AIC, and will report results from the non-linear model if the AIC suggests that the nonlinear model provides a better fit. In this case, the primary comparison will involve a comparison of the estimated means of the two groups at each time point, and will be displayed in a table similar to the following:

Table 7.3: Model based estimates of BPF over time

Visit	Model Based		p-value for difference
	Ibutilast	Placebo	
Baseline Estimate (SE) 90% CI	xx (xx) (xx, xx)	xx (xx) (xx, xx)	0.xx
Week 24 Estimate (SE) 90% CI	xx (xx) (xx, xx)	xx (xx) (xx, xx)	0.xx
Week 48 Estimate (SE) 90% CI	xx (xx) (xx, xx)	xx (xx) (xx, xx)	0.xx
Week 72 Estimate (SE) 90% CI	xx (xx) (xx, xx)	xx (xx) (xx, xx)	0.xx
Week 96 Estimate (SE) 90% CI	xx (xx) (xx, xx)	xx (xx) (xx, xx)	0.xx

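### SAP 7.1 reads the sign of its primary BPF contrast backwards, so a benefit of ibudilast would be declared as faster BPF change

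*Combined protocol and SAP*

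**What the plan says.** SAP 7.1 sets up the primary analysis as a linear mixed model with a common intercept and one slope per arm.

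- The outcome Y "is the BPF value for the" subject and time point, so it is neither a loss nor an absolute change.
- The parameters of interest are β₃ and β₄, "which correspond to the estimated slopes in the treatment and placebo groups, respectively".
- The null hypothesis is "\theta_1 = \beta_4 - \beta_3 = 0", tested against a two-sided alternative. θ₁ is therefore the placebo slope minus the ibudilast slope.
- After a rejection, the sign of θ₁ gives the conclusion. If θ₁ "is greater than zero, then we will conclude that the study provides evidence that the rate of BPF change is slower in the Ibudilast" group; if θ₁ "is less than zero, then we will conclude that the study provides evidence that the rate of BPF change is faster in the Ibudilast" group.

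Protocol 12.1.2 defines its contrast the other way round, as treatment minus placebo: "\delta = \beta_T - \beta_P".

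SAP 2.1 defines BPF as parenchymal volume divided by the volume inside the brain's outer surface. It describes atrophy as progressive, "with a mean rate in untreated MS patients generally ranging from 0.5-1.5% per year", and cites treatment effects "including a 34% slowing of atrophy in a phase II trial of Ibudilast in RRMS".

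**The concern.** A two-sided rejection does not say which arm did better. Under the linear primary model, the two sentences after the test are the only rule in the SAP that turns a rejection into a direction. BPF goes down as the brain shrinks, so a treatment that works has the less negative slope, and placebo minus ibudilast is then negative. The SAP attaches the unfavourable conclusion to that sign.

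Followed literally, a significant benefit on the primary endpoint would be declared as faster BPF change on ibudilast, and a significant harm as slower change. SAP 8.2 says that the MTR comparison proceeds as in 7.1, so the reversed rule goes with it. SAP 11.2 gives a nominal p-value for concluding efficacy at the interim look but no direction of its own. If the 7.1 sign convention were borrowed there, the interim reading would be exposed to the same error.

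**Working it through.** There is no stated figure to reproduce, because the point is a sign rule.

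**Inputs**
- Y is the BPF value; β₃ is the ibudilast slope, β₄ the placebo slope, and θ₁ = β₄ − β₃ (SAP 7.1).
- BPF falls with atrophy (SAP 2.1), and benefit is a reduction in the rate of deterioration (SAP 9.1).
- Untreated loss is 0.5 to 1.5% per year. Slowing is 34% in the earlier ibudilast trial, within a range of 30 to 50% for available therapies (SAP 2.1).
- Brain volume change on placebo was −1.2% at 12 months, with about 35% attenuation at 60 mg/d (Protocol 4.7). This is percent brain volume change, a different measure from BPF, and it is used here only for its sign.

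**Algebra**

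Write the placebo slope as β₄ = −r with r > 0, and the ibudilast slope as β₃ = −(1 − s)r, where s is the fraction of slowing. Then

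θ₁ = β₄ − β₃ = −r + (1 − s)r = −sr.

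This is negative whenever s > 0 (benefit) and positive whenever s < 0 (harm).

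**Numbers (% per year)**

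| Source | r | s | β₄ | β₃ | θ₁ | SAP 7.1 conclusion on ibudilast |
|---|---|---|---|---|---|---|
| SAP 2.1 | 0.5 | 0.34 | −0.50 | −0.33 | −0.17 | faster |
| SAP 2.1 | 1.5 | 0.34 | −1.50 | −0.99 | −0.51 | faster |
| SAP 2.1, smallest effect | 0.5 | 0.30 | −0.50 | −0.35 | −0.15 | faster |
| SAP 2.1, largest effect | 1.5 | 0.50 | −1.50 | −0.75 | −0.75 | faster |
| Protocol 4.7 | 1.2 | 0.35 | −1.20 | −0.78 | −0.42 | faster |
| Harm (assumed 10% faster loss) | 1.2 | −0.10 | −1.20 | −1.32 | +0.12 | slower |

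Over 96 weeks (96/52 = 1.846 years) the first two rows become −0.31 and −0.94 percentage points. Every benefit is labelled faster, and the harm is labelled slower.

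**Chance of each conclusion**

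Take a true benefit with 80% power at two-sided α = 0.10. The expected |Z| is 1.645 + 0.842 = 2.486, in the negative direction. The probability of rejecting with θ₁ < 0, and so of declaring faster change on ibudilast, is Φ(2.486 − 1.645) = 0.80. The probability of rejecting with θ₁ > 0 is 1 − Φ(2.486 + 1.645), about 0.00002.

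**Check of the coding**

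A model with a common intercept, arm-specific slopes and random intercept and slope (stratum terms omitted) was fitted to one simulated trial. The assumptions were 250 subjects, five visits, baseline BPF 0.80, 1% yearly loss on placebo and 34% slowing. The SDs were 0.03 for the intercept, 0.00003 per week for the slope and 0.0016 for the residual. In units of BPF × 100 per 96 weeks, β₃ was −0.958, β₄ was −1.428 and θ₁ was −0.470. The simulated benefit again has θ₁ below zero.

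**The case against.** The best defence is that the authors were thinking of positive rates of loss. SAP 2.1 quotes atrophy as a positive percentage per year, and SAP 9.1 describes the effect as a reduction in deterioration. If β₃ and β₄ were positive loss rates, placebo minus ibudilast above zero would indeed mean slower loss on ibudilast. That probably explains how the text arose, and it points to a drafting slip rather than a disputed method. It does not rescue the rule. The coefficients multiply time in a model for the BPF value, and nothing in the SAP redefines them as loss or reverses their sign.

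Three further points limit the consequence, and they stand:

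- Nothing computed changes. Table 7.1 shows BPF by arm and visit, and Table 7.2 shows both arm slopes with 90% intervals, so a reversed statement would contradict the tables beside it. An unnoticed misreport is unlikely.
- The rule applies only to the linear model. If the AIC favours categorical time, SAP 7.1 compares group means at each visit and draws no θ₁ conclusion.
- Only SAP 8.2 expressly reuses the comparison. SAP 8.1, 8.3 and 8.4 refer to a similar model without restating the directional sentences, so extending the correction to them is a precaution.

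**Conclusion.** The point holds. On the SAP's own definitions, both directional conclusions for the primary endpoint are reversed under the linear model. The result needs only that BPF declines in both arms, which the documents assume throughout. It does not depend on the assumed baseline BPF, the variances or the size of the effect.

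The error is one of sign: a 34% slowing appears as θ₁ = −0.17 to −0.51% per year and would be declared as faster change. Estimates, intervals, the two-sided p-value, α and sample size are untouched. The error is visible to anyone who compares the sentence with Table 7.2. It should still be corrected, because it is the pre-specified conclusion for the primary endpoint and it states the opposite of what the data would show.

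**What to change.** Make one of two equivalent changes in SAP 7.1:

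1. Define θ₁ = β₃ − β₄ (ibudilast minus placebo), as the protocol does with δ, and leave the two conclusions as they are.
2. Keep θ₁ = β₄ − β₃ and exchange slower and faster in the two conclusions.

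The first is preferable because it also aligns the SAP with Protocol 12.1.2.

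Then state in SAP 8.2 that the corrected reading applies to MTR. SAP 3.2 links lower MTR to loss of myelin and axons, so the same reversal arises there. Add one line giving the favourable direction for each outcome in 8.1, 8.3 and 8.4 wherever the rule is reused. It may differ by outcome: SAP 3.1 associates a fall in radial diffusivity with possible remyelination.

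Separately, the rejection rule in SAP 7.1 reads as |Z| less than the critical value. Check this symbol, and the order of the terms in the contrast, against the source PDF. If the less-than sign is really there, change it to greater-than. The finding on direction does not rest on that symbol.

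The cost is wording only: one contrast or two sentences, plus the direction lines. Data, model, estimates, p-value and sample size do not change.

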8.8. Assessments

Table 1: Schedule of Assessments

Table 2: Schedule of Unplanned Procedures and Assessments

Figure 12: Study Design

Visits Week 4, 8, 24, 48, 72, and 96 will have a window of ± 5 days. Safety visits conducted at Week 12, 36, 60, 84 and 100 will have a window of ± 14 days. (See Table 1 Schedule of Assessments)

Clinical laboratory evaluations will be performed by a central laboratory. All clinical and laboratory evaluations, procedures related to inclusion/exclusion criteria, or performed during treatment must be reviewed, initialed and dated by the Principal Investigator or appropriate designee listed on Form FDA 1572.

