8.8.2.9. Brain Magnetic Resonance Imaging (MRI)

Brain MRI will be performed in a standard fashion, as outlined in the MRI procedure manual. Each subject's baseline MRI must be approved by the MRI Reading Center prior to randomization.

Brain MRIs will be read clinically for non-MS pathology by a board-certified neuroradiologist, with a report entered into the study database within ten days and reported back to the treating neurologist through standard clinical results reporting methods. Urgent findings identified on brain MRI will be reported to the treating neurologist immediately at the discretion of the reading neuroradiologist.

At any time during the study, subjects who received unscheduled corticosteroid treatment must postpone their MRI until 1 month after completion of the corticosteroid treatment.

All sites will perform a test (or "dummy") MRI scan prior to study initiation. This test MRI will ensure adequate performance of the study MRI.

It is required that the same MRI scanner be used to acquire all MRI scans over the course of the study. If during the study period a study site needs to change the MRI scanner or the current MRI scanner undergoes significant upgrades (hardware or software), the investigator should notify the Clinical Coordinating Center. For all changes in scanner and significant scanner upgrades, the investigator will be requested to obtain MRI scans of 4 volunteers acquired prior to changing/upgrading the MRI scanner and the same 4 volunteers again after changing scanners (a total of 8 scans). The site will be allowed to acquire ibudilast trial subject scans on the new scanner only after obtaining approval of the new or upgraded scanner.

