The primary outcome of this trial is WBA, estimated as the change in brain parenchymal fraction (BPF). BPF is a normalized measure of whole brain volume calculated as the volume of brain parenchymal tissue divided by the total volume within a smoothed outer surface of the brain (Rudick et al, 1999). The fully-automated algorithm takes partial volume effects into account, can utilize either FLAIR or dual echo PD-/T2-weighted images, and has a scan-rescan coefficient of variability < 0.2%. Sensitivity analyses for BPF include SIENA and an advanced SIENA technique that utilizes a single longitudinally co-registered image within each patient, which may further reduce variability.

For the purposes of this trial, BPF will be computed based on MRI scans performed at screening, and at weeks 24, 48, 72, and 96. The images will be processed, and reviewed for quality and completeness at the Cleveland Clinic MS MRI Analysis Center. Images will be checked for adherence to protocol, consistency over time, image quality, and completeness of the electronic transfer. This step determines if the MRI data set can be approved for BPF analysis or if it should be rejected, reacquired, or resent from NeuroRx. Once approved, the images will be set up to be analyzed. The image analysis pipeline automatically records numerical results in an internal database. Database records for which the atrophy results have been visually verified will be transmitted to the NeuroNEXT Data Coordinating Center (DCC) in accordance with the procedures outlined in the corresponding data transfer agreement.

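### In the categorical-time BPF model, scans done outside a scheduled visit are labelled with the next visit rather than the nearest, so late and early-withdrawal scans show too little atrophy for their label

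*Combined protocol and SAP*

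**What the plan says.** The primary analysis in SAP 7.1 is a linear mixed model with time in weeks and a contrast between the two arms' slopes. To check linearity, "non-linear trends will be modeled by inserting time as a categorical variable". For that model the SAP adds that "visits that were performed outside of an expected scheduled visit will be categorized into the next expected scheduled visit". It compares the two models by AIC and "will report results from the non-linear model if the AIC suggests that the nonlinear model provides a better fit". In that case the arm means at each visit become the primary comparison (SAP Table 7.3, with rows for Baseline and Weeks 24, 48, 72 and 96).

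On the scan schedule, SAP 2.1 says that "BPF will be computed based on MRI scans performed at screening, and at weeks 24, 48, 72, and 96". Protocol 8.8 says "Visits Week 4, 8, 24, 48, 72, and 96 will have a window of ± 5 days". Protocol 8.8.2.9 says that "subjects who received unscheduled corticosteroid treatment must postpone their MRI until 1 month after completion of the corticosteroid treatment". Protocol Table 2 and the Early Withdrawal list in 8.8.1 include a brain MRI for patients who stop study drug and decline semi-annual follow-up, at whatever week that happens. The Week 100 safety visit has no MRI (Protocol Table 1).

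The SAP does not define when a visit counts as outside its schedule. It gives no rule for two scans in one category and none for a scan after Week 96.

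**The concern.** The protocol itself generates off-schedule scans, and the rule moves all of them in one direction. A scan taken shortly before a planned visit goes to the right category. A scan taken shortly after one is carried forward to a visit that may be almost six months away. Because BPF falls over time, a scan labelled later than it was taken shows less atrophy than its label implies, so visit means are flattened.

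If both arms are equally affected, the visit-wise difference shrinks a little. If one arm has more early withdrawals or more steroid-treated relapses, its atrophy looks slower for a reason unrelated to the drug's effect on the brain. Early discontinuation is itself a tolerability endpoint here, so balance between arms cannot be taken for granted. At stake are the linearity check and, if AIC prefers the categorical model, the reported primary comparison.

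**Working it through.** The plan states no figure that depends on this rule, so there is nothing to reproduce. I applied the rule to the plan's own schedule.

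**Inputs from the documents.** MRI at Weeks 24, 48, 72 and 96 (SAP 2.1); window ±5 days (Protocol 8.8); MRI delayed to 1 month after steroids (Protocol 8.8.2.9); 125 per arm and 10% dropout (SAP 9.1); atrophy of 0.5-1.5% per year and 34% slowing in the earlier ibudilast trial (SAP 2.1).

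**Assumptions.** 1 month = 28-31 days; every dropout has an Early Withdrawal MRI, with timing spread evenly over the four intervals; 5-10% of patients with one postponed scan. The documents give no rate of late scans or treated relapses.

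**1. Early Withdrawal scans.** The gap between scan and label is 0-24 weeks, with mean 12 if uniform.
- Per arm: 125 × 0.10 = 12.5 withdrawals; 12.5 / 4 ≈ 3.1 per category.
- Week 48 cell: 125 − 6.25 = 118.75 genuine scans plus 3.125 moved scans ≈ 121.9.
- Shift in mean time: 3.125 × 12 / 121.9 ≈ 0.31 week; 0.31 / 48 ≈ 0.6%.

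**2. A steroid-postponed scan, if 'outside' includes scans beyond the window.**
- Steroids ending on the nominal Week 24 day put the scan at Week 28.0-28.4, that is +28 to +31 days against ±5.
- The nearest MRI visit is Week 24, about 4 weeks back. The next visit with a BPF category is Week 48, about 20 weeks ahead. (Read literally, the next clinic visit is Week 36, which has no MRI.)
- Steroids ending 25 days before to 5 days after the nominal day give scans at about Weeks 24.4-29.1. A few stay within ±5 days and are not moved.
- The same delays at Week 96 give about Weeks 96.4-101.1, with no later category.

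Loss missing from one Week 28.3 scan labelled Week 48 = r × (48 − 28.3)/52. The Week 48 treatment difference under 34% slowing = 0.34 × r × 48/52.

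| r per year | Missing loss, one scan | Week 48 difference |
|---|---|---|
| 0.5% | 0.19% | 0.16% |
| 1.0% | 0.38% | 0.31% |
| 1.5% | 0.57% | 0.47% |

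**3. Group effect of postponed scans.** Suppose a fraction f of an arm contributes one such scan in addition to its real Week 48 scan. The simple cell mean then shifts by r × (19.7/52) × f/(1+f) in placebo and 0.66 times that in the active arm. With r = 1.0%, the true difference is 0.3138.

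| f placebo, f active | Shift placebo | Shift active | Difference | Change |
|---|---|---|---|---|
| 5%, 5% | 0.0180 | 0.0119 | 0.3077 | −2.0% |
| 10%, 10% | 0.0344 | 0.0227 | 0.3021 | −3.7% |
| 10%, 5% | 0.0344 | 0.0119 | 0.2913 | −7.2% |
| 5%, 10% | 0.0180 | 0.0227 | 0.3185 | +1.5% |

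The percentage changes do not depend on r, which cancels. These are simple cell means; the mixed model would weight the records differently.

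**4. Nearest-visit rule.** Every postponed scan in step 2 returns to Week 24 or Week 96, at most about 5 weeks from nominal. Under the SAP rule, the moved Week 24 scans sit about 19-23 weeks from their label.

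**The case against.** The strongest reply is that the rule speaks of visits, not late scans. The protocol postpones the MRI belonging to a scheduled visit, and the postponement footnote in Protocol Table 1 sits on the scheduled MRI cells. A postponed Week 24 scan may therefore simply stay the Week 24 scan. The natural target of the rule would then be the unplanned visits of Protocol Table 2. Relapse evaluations have no MRI, which leaves Early Withdrawal. On that reading the Week 24 and Week 96 examples and the duplicates disappear, because a withdrawn patient has no later scan. This stands as a fair reading, and the text does not decide between the two. Early Withdrawal scans are mis-timed on either.

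It is also right that the rule is confined to the categorical model. A reader might infer that the primary slope test is damaged. The documents do not support that, because the rule is introduced for the categorical approach alone. The SAP does not, however, say whether the linear model's weeks are actual or nominal.

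A reader might also infer that mislabelling steers AIC towards the categorical model. That is unsupported. The labels enter only that model, and if change is linear in actual time, wrong labels worsen its fit. They could mask real curvature, which weakens the check in the other direction.

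**Conclusion.** The rule is stated, not merely missing detail, and it times foreseeable scans worse than a nearest-visit rule would. It should be changed, but the expected effect is small. With Early Withdrawal scans alone, at the planned 10% dropout spread evenly, the Week 48 mean time moves by about 0.6%. If late scans are included and 5-10% of each arm is affected equally, the Week 48 difference shrinks by about 2-4%. The unequal cases tried ran from −7.2% to +1.5%. The affected fractions are assumptions. The consequence for the reported result is conditional on AIC choosing the categorical model.

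Two stronger readings should be resisted. The loss missing from one Week 28 scan is about 1.2 times the Week 48 treatment difference, which might suggest that the treatment effect is swamped. But that is one record's timing error, which can occur in either arm, set against a between-arm mean. Nor do the documents say that postponed Week 96 scans are discarded: the SAP is silent on them.

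**What to change.** Replace the sentence in SAP 7.1 with: 'For the categorical-time model each post-baseline MRI is assigned by actual scan date to the nearest scheduled MRI visit (Week 24: after baseline to Week 36; Week 48: >36 to 60; Week 72: >60 to 84; Week 96: >84, open-ended). If two scans fall in one window, the one closest to the target week is used.' Also state that the linear model uses actual scan dates and includes all scans. If categorical-time versions are fitted for the major secondary MRI outcomes, use the same windows.

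The cost is a short SAP edit, with no new data. There is a small downside. An occasional duplicate, such as an Early Withdrawal scan at Week 30 after a Week 24 scan, is not used in the categorical model. Very early withdrawal scans are still labelled Week 24. The polynomial check in Protocol 12.1.2 needs no visit categories and would avoid both.
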